1. The research clearly supports the practice of immediate skin to skin after vaginal birth; therefore, we anticipate this intervention to have similar benefits after cesarean birth. KUMC is a designated Baby-Friendly hospital. The Baby-Friendly designation process requires verification of policies, curriculum, action plans, quality improvement projects, staff training, and competency verification, as well as a readiness interview and an on-site survey. When implementing immediate StS after vaginal deliveries, the healthcare providers went through training which included techniques to educate and prepare parents. Immediate StS is now standard for all vaginal deliveries at KUMC.
2. Kangaroo care in the OR is understudied and therefore this project will hopefully advance our understanding and comfort with this procedure.
3. We anticipate that implementing immediate StS after cesarean deliveries will benefit both moms and babies.

II. Research Plan and Design

A.Study Objectives: Aim: Assess the maternal and infant benefits of kangaroo care in the OR. Randomize women to receive standard OR fetal resuscitation versus immediate skin to skin after scheduled cesarean deliveries of term, singletons. Hypothesis: Immediate skin-to-skin (StS) during cesarean section will decrease the number of pain and anxiolytic medications required during surgery, decrease the maternal rating of pain during cesarean section, and increase the maternal satisfaction score of cesarean section. We hypothesize there will be no difference in the 5-minute Apgar score, neonatal admission to the ICU, maternal infection rate, or QBL between the two groups.

B.Study Type and Design: Randomized controlled trial (RCT).

C.Randomization will be done by simple randomization. Subjects will be assigned into two groups A and B. Subjects will be assigned to each group purely randomly for every assignment. Randomization will be performed by using an excel file, available here in a read only state: <http://cafe.naver.com/easy2know/6427>. Allocation concealment will be done with sealed envelopes.

1. Blinding of the physicians, nurses, and study participants is not possible in this study. We do plan to blind the statistician to the treatment. (S)he will not know the treatment name because the treatment name will be hidden, as in A and B.

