2. Approximately 300 scheduled, term singleton cesareans are performed annually at KU. Our primary outcome is to detect at 20% difference in satisfaction with the procedure. Power calculation as below:
 - Total n=112 (56 per group)
 - Assumptions
 - o Alpha=0.05 (95% confidence interval)
 - o Beta=0.20 (80% power)
 - o Control group mean (SD) satisfaction 4.0 (1.5)
 - o Experimental group mean (SD) satisfaction 4.8 (1.5)

D. Subject Criteria (See Vulnerable Populations appendix, if applicable): All patients presenting for delivery at KUMC will be considered as study subjects regardless of race, age, or primary language.

1. Inclusion criteria: All term, singleton scheduled cesarean sections occurring at KUMC.
2. Exclusion criteria: Priority, urgent and emergent cesareans. Planned general anesthesia, fetal anomalies, fetal aneuploidy/genetic syndrome, abnormal fetal dopplers, placental previa, placenta accreta, multiple gestations, preeclampsia with severe features.
3. Withdrawal/Termination criteria: Standard fetal resuscitation protocols will be utilized. There are times where the infant will be brought to the warmer for infant or maternal indications. Examples of infant indications are abnormal vital signs. Maternal indications would include uncontrolled pain or surgical complication.
4. Our patients can be enrolled in studies that involve collection of cord blood after delivery. No studies are currently going on that impact the mode of delivery or infant resuscitation.

E. Specific methods and techniques used throughout the study

1. Laboratory tests: Likert scale for maternal satisfaction and pain scores. Anesthesia record will be analyzed for medications given to mom both before, during and after the cesarean delivery as part of the procedural care. Fetal apgars, skin to skin timing and NICU admission will be obtained from the pediatric nursing records.
2. Study Procedures: Standard, preexisting neonatal resuscitation protocols already in use at KUMC.
3. Routine neonatal care will be utilized in both the control (baby to warmer, delayed StS) and treatment (baby to maternal chest, immediate StS) groups.

F. Risk/benefit assessment:

1. Physical risk - none anticipated
2. Psychological risk – Our current standard of bringing the baby to the warmer after cesarean birth is hypothesized to result in more maternal anxiety compared to the treatment group receiving immediate StS.
3. Social risk - none anticipated
4. Economic risk - none anticipated

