5. Potential benefit of participating in the study
 - a. The chance to be randomized to receive immediate StS with newborn and gain the known benefits associated with kangaroo care.
 - b. A change in standard practice to improve maternal and newborn care.
 - c. Published literature or poster presentation may encourage other institutions to consider immediate StS after cesarean delivery.

G. Location where study will be performed: KUMC labor and delivery.

H. Collaboration (with another institution, if applicable): n/a

I. Single IRB Review for a Multi-site study (if applicable): n/a

J. Community-Based Participatory Research (if applicable) – n/a

K. Personnel who will conduct the study, including:

1. Indicate, by title, who will be present during study procedure(s): Routine care will be performed by the physician, nurses, and techs at KUMC.
2. Primary responsibility for the following activities, for example:
 - a. Determining eligibility: PI
 - b. Obtaining informed consent: Clinical Research Coordinator
 - c. Providing on-going information to the study sponsor and the IRB: PI
 - d. Maintaining participant's research records: Clinical Research Coordinator
 - e. Completing physical examination: the physicians performing cesarean delivery as part of standard care.
 - f. Taking vital signs, height, weight: the nurses and physicians providing routine care to mom and newborn.
 - g. Drawing / collecting laboratory specimens: the nurses and physicians providing routine care to mom and newborn.

- h. Performing / conducting tests, procedures, interventions, questionnaires: the nurses and physicians providing routine care to mom and newborn.
- i. Completing study data forms: the nurses and physicians providing routine care to mom and newborn.

Managing study database: PI and Clinical Research Coordinator.

L. Assessment of Subject Safety and Development of a Data and Safety Monitoring Plan

- 1. n/a – no more than minimal risk. As per routine care, if StS is determined to be unsafe based on maternal or baby status, it will be terminated at the request of the obstetrician or newborn nurse based on the same standards we use for routine StS practice.
- 2. If adverse events happen with routine care, they will be reported to the PI and communicated to the IRB. As with any adverse healthcare events, a safety incident (SI) report will be generated by KUMC staff.

III. Subject Participation

A. Recruitment:

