2. All collected information will be de-identified. A code with subject numbers and their corresponding MRNs will be kept in an excel spreadsheet on the P drive.
3. Participants will be assigned a subject number, not identified by name/dob/mrn.
4. The research coordinator will keep the excel spreadsheet code on the p drive.
5. The patient's assigned research participant number (as assigned by the research coordinator after recruitment) will be included in the research tab in the electronic health record. This participant number will be used when the subject's data is entered into redcap survey.
6. Data stored in redcap survey.
7. Mobile devices - n/a
8. No data sent outside KUMC

B. **Sample / Specimen Collection:** n/a

C. **Tissue Banking Considerations:** n/a

D. **Procedures to protect subject confidentiality:** n/a

E. **Quality Assurance / Monitoring**

- 1.Data taken from the electronic health record will be used.
- 2.No third-party monitoring.

V. **Data Analysis and Reporting**

A. **Statistical and Data Analysis:** Participant demographics will be summarized using descriptive statistics (proportions and means). Differences between study groups will be assessed using chi-square and t-tests for categorical and continuous variables, respectively. Differences in satisfaction and pain scores between study groups will be assessed using t-tests if the data is normally distributed. If not normally distributed, data will be adjusted by taking the log of the mean scores, or a non-parametric comparison of medians will be conducted. If any clinically important differences exist between the experimental and control groups at baseline, a linear regression model will be constructed allowing us to control differences between groups.

B. **Outcome:** Primary outcome is maternal satisfaction. Improvement in maternal satisfaction with the cesarean delivery will be the criteria for success. We set clinically meaningful difference of 20% improved satisfaction.

C. **Study results to participants:** none

D. **Publication Plan:** Our goal is to publish our RCT in either AJOG or ACOG journals.

VI. Bibliography / References / Literature Cited (choose the applicable title and list citations according to APA or other accepted style in your discipline)

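### The self-rated primary outcome is assigned to unblinded care staff to collect with no stated safeguard, and no rule keeps skin-to-skin timing from the blinded statistician

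*Combined protocol and SAP*

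**What the plan says.** **Outcome.** Section V.B states "Primary outcome is maternal satisfaction" and makes its improvement the criterion for success. The instrument, in II.E.1, is given only as "Likert scale for maternal satisfaction and pain scores".

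**Blinding.** II.C.1 says "Blinding of the physicians, nurses, and study participants is not possible in this study". The one person to be blinded is the statistician, of whom it says "S)he will not know the treatment name because the treatment name will be hidden, as in A and B".

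**Who collects.** II.K.2.h reads "Performing / conducting tests, procedures, interventions, questionnaires: the nurses and physicians providing routine care to mom and newborn". II.K.2.i reads "Completing study data forms: the nurses and physicians providing routine care to mom and newborn". The Clinical Research Coordinator is given consent and research records, and shares management of the database with the principal investigator, but is not named for outcome collection. IV.A refers to a REDCap survey without saying who fills it in.

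**Timing data.** II.E.1 adds "Fetal apgars, skin to skin timing and NICU admission will be obtained from the pediatric nursing records". II.E.3 separates the arms by delayed versus immediate skin-to-skin contact.

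**The concern.** When participants know their arm, a self-rating is open to bias from two sources: the woman's own expectation, and the circumstances in which she is asked. The first cannot be designed away here. The second can, yet the plan leaves it with people who know the allocation and are caring for the woman and her baby. A woman who gives her rating to those staff, or within their sight, may answer more kindly, and the degree of kindness may depend on the arm. Such a shift cannot be told apart from a benefit afterwards, and it would fall on the only outcome for which the trial is powered.

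The statistician's mask matters because V.A leaves choices to be made once the data are in hand: t-test, log transformation or a non-parametric comparison, and a regression model if baseline differences are judged clinically important. A masked analyst makes those choices without knowing which arm they favour. A variable that records when skin-to-skin began would identify the arms at a glance.

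**Working it through.** **Inputs.** From II.C.2: 56 per group, SD 1.5 in both groups, means 4.0 and 4.8 (difference 0.8), alpha 0.05, power 80%. The size of any reporting bias is not in the documents; the values below are assumptions.

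**1. Reproduce the plan's sample size.** Per arm, n = 2 × (1.960 + 0.842)² × 1.5² / 0.8² = 55.2, rounded up to 56, total 112. This matches the plan with a two-sided test; a one-sided test would need 44 per arm. Power at 56 per arm is 0.806 by the normal formula and 0.799 by the t-test. The concern does not alter the sample size.

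**2. Standard error and significance threshold.** SE = 1.5 × √(2/56) = 0.283. The smallest significant difference is 1.96 × 0.283 ≈ 0.556 (normal), or about 0.562 with the t critical value.

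**3. False-positive rate under an assumed bias b with no true effect.** P(significant in favour of skin-to-skin) = 1 − Φ((0.562 − b)/0.283).

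| Assumed bias b (points) | Share of control mean 4.0 | Share of target 0.8 | Rate favouring skin-to-skin, threshold 0.562 | Same, threshold 0.556 | Two-sided, threshold 0.556 |
|---|---|---|---|---|---|
| 0 | 0% | 0% | 2.5% (nominal) | 2.5% | 5.0% |
| 0.2 | 5% | 25% | 10% | 10.5% | 10.9% |
| 0.3 | 7.5% | 37.5% | 18% | 18.4% | 18.5% |
| 0.4 | 10% | 50% | 28% | 29.2% | 29.2% |

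Example for b = 0.3: (0.562 − 0.3)/0.283 = 0.926, and 1 − Φ(0.926) ≈ 0.18.

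Here b is total between-arm reporting bias from every source. The documents give no way to split it into a collector part and an expectation part.

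**4. The mask, by comparison of sections.** II.C.1 hides the treatment name behind A and B. II.E.3 defines the arms by when skin-to-skin begins. II.E.1 collects that time. V.A does not name timing as an analysis variable, and no section says whether the statistician receives it. So the mask fails if timing is in the file at the primary analysis and is not threatened by timing if it is absent. The plan does not settle which.

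**The case against.** Several stronger readings are tempting, and the documents do not carry them.

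- A reader might infer that satisfaction is asked face to face. The text never says so. II.K.2 is a list of responsibilities, and handing the woman a form or a REDCap link would fit it.
- A reader might infer that the operating team collects the score. II.K.2.e names the physicians performing the cesarean for the physical examination; item h names the wider group giving routine care.
- A reader might infer that the collectors favour skin-to-skin. Favourable views are recorded for the investigators and for several obstetricians (I.B), not for bedside staff at large, and I.B and I.C imply that some are not yet comfortable with the practice.
- A reader might infer from II.F.5.a, "The chance to be randomized to receive immediate StS with newborn and gain the known benefits associated with kangaroo care", that women are told of established benefit. That is the protocol's risk and benefit text. The consent pages are not available, so what women are told is unknown.
- A reader might infer that the statistician's mask has already failed. It can be broken, but nothing shows that the statistician gets timing before the primary analysis.

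It is also fair to say that the illustration would apply to any bias in any trial with this standard error, and that private completion leaves the mother's expectation or disappointment untouched. Both points stand, and they limit the claim. They do not answer the core of it: the only text on who conducts questionnaires names unblinded care staff, and no section supplies a safeguard.

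**Conclusion.** The point holds as a cheap improvement to a stated arrangement. It is not an error in the sample size, and it is not evidence that results would be biased. The plan gives collection of a subjective, unblinded primary outcome to care staff who know the arm, without stating mode, time or privacy. It also claims a mask for the statistician without the data rule needed to keep it.

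The figures in the working are a sensitivity range. They rest on the plan's SD of 1.5 and 56 per arm, on no true effect, and on bias sizes that are assumed. They show that a bias of a quarter to a half of the target difference would matter. They do not show that such a bias will occur, or how much of it the change below would remove.

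**What to change.** **II.K.2.h (and i).** State that the woman completes the satisfaction item herself, in REDCap or on paper, at one fixed postpartum time that is the same in both arms, without care staff present and without their seeing the answers. Provide translated forms, or an interpreter from outside the care team, because II.D enrols women whatever their primary language.

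**Pain rating.** Leave its timing unchanged. The hypothesis in I.A and II.A concerns pain during the cesarean, and moving the item to the postpartum period would turn it into recalled pain.

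**II.C.1.** Add that skin-to-skin timing and warmer-transfer fields are withheld from the statistician until the primary analysis is locked.

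**Cost.** REDCap is already the study database and is used for telephone consent, so the main work is a survey form and an extract rule. The downsides are possibly a few more missing surveys, for which the coordinator can send one reminder, some translation work, and an update to the mobile-devices entry in IV.A.7, now marked not applicable, if a tablet is used.

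### The primary t-test hangs on an undefined normality check, and its fallback is a log rule that cannot be run as written or a comparison of medians, with no rule for choosing between them

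*Combined protocol and SAP*

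**What the plan says.** Section V.B makes maternal satisfaction the primary outcome and sets a 20% improvement as the clinically meaningful difference. Section II.C.2 sizes the trial on arithmetic means: 4.0 in the control group and 4.8 in the experimental group, SD 1.5 in each, alpha 0.05, 80% power, 56 per group. Section II.E.1 describes the measure only as "Likert scale for maternal satisfaction and pain scores", without the number of points or the range.

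The analysis rule is in V.A. Its first step is "Differences in satisfaction and pain scores between study groups will be assessed using t-tests if the data is normally distributed". Its second step is "If not normally distributed, data will be adjusted by taking the log of the mean scores, or a non-parametric comparison of medians". V.A does not say how normality is judged, on which data, or at what threshold. It does not say when the log is used rather than the medians, or which non-parametric test is meant. Neither V.A nor V.B says how a log or median result is to be held against the 20% criterion.

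**The concern.** The rule governs the trial's only success criterion, and it has three separate faults.

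- **One branch cannot be carried out as worded.** Averaging first and logging afterwards transforms no data. The natural repair, logging each score, is a remedy for right skew; on scores bounded above it tends to lengthen the lower tail.
- **The choice is open until the data are seen.** An unstated normality criterion followed by an unresolved choice of fallback lets several p-values compete for the primary result.
- **The target moves.** The sample size is for a difference in means. A log analysis estimates a ratio of geometric means, and a median or rank comparison estimates something else again.

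At stake is whether the reported primary result is the comparison the trial was sized for, at the stated error rate.

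**Working it through.** **1. Reproduce the sample size.** Inputs from II.C.2: difference δ = 4.8 − 4.0 = 0.8, SD σ = 1.5, alpha 0.05, power 0.80. Sidedness is not stated.

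n per group = 2(z₀.₉₇₅ + z₀.₈₀)²σ²/δ² = 2 × (1.960 + 0.842)² × 2.25/0.64 ≈ 55.2, so 56.

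The plan's figure is reproduced with a two-sided test; a one-sided test would give 44. Exact power of the two-sample t-test at 56 per group is 79.9%. The arithmetic is sound, and it belongs to a t-test on raw means.

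**2. The log rule taken literally.** ln 4.0 = 1.386 and ln 4.8 = 1.569; the difference is 0.182 = ln 1.2. That is one number per arm, with no distribution changed and nothing to test.

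**3. Which scales are possible.** On a scale from a to b with mean m, the largest possible SD is √[(b − m)(m − a)]. At m = 4.8 on 1–5 this is √(0.2 × 3.8) = 0.87, and on 0–5 it is √(0.2 × 4.8) = 0.98. Both are below 1.5, so the planning values need a longer scale. The scales 1–6, 1–7 and 1–10 are assumed below.

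**4. The log rule read as logging each score.** Integer scores were given the planned means and SD, with probabilities proportional to the exponential of a quadratic in the score (an assumed shape). Skewness before and after logging:

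| Scale | Control arm | Treated arm |
|---|---|---|
| 1–6 | −0.34 to −1.22 | −1.17 to −1.97 |
| 1–7 | 0.00 to −1.08 | −0.37 to −1.47 |
| 1–10 | 0.16 to −1.03 | 0.05 to −1.18 |

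Logging increases the size of the skew in every case. The estimated quantity becomes a geometric-mean ratio, 1.22 to 1.23 here. If a scale includes 0, the log of that score does not exist; V.A applies the same rule to pain scores, whose range is also not given.

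**5. Power and type I error.** 4,000 simulated trials per row, 56 per arm, two-sided 0.05. Monte Carlo standard error is √(0.8 × 0.2/4000) = 0.6 points for power and √(0.05 × 0.95/4000) = 0.3 points for type I error. A repeat run agreed to within about one point.

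| Scale | Power: t-test | Power: log t-test | Power: rank-sum | Type I: t-test | Type I: log t-test | Type I: smaller of log and rank p |
|---|---|---|---|---|---|---|
| 1–6 | 78.3% | 60.3% | 87.5% | 4.3% | 4.8% | 6.2% |
| 1–7 | 79.7% | 73.3% | 79.3% | 5.3% | 5.2% | 6.9% |
| 1–10 | 79.9% | 78.4% | 78.2% | 5.0% | 4.9% | 6.1% |

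In the last column the smaller p-value is taken after a failed normality check.

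**6. How often the fallback would be reached.** If normality were judged by Shapiro-Wilk at 0.05 in each arm (an assumption), at least one arm failed in 99.8% to 100% of these trials. Whole-number scores with few levels almost always fail such a test at 56 per arm, whether or not the t-test is in difficulty. The t-test columns above show that it is not.

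**The case against.** The strongest defence is that the rule is loosely worded but conventional. The t-test comes first. Any analyst would read the log phrase as logging individual scores, and a comparison of medians is common shorthand for a rank-sum test. On those readings each branch, taken alone, holds its error rate: 4.8% to 5.2% for the log t-test. The rank-sum test reaches 78% to 88% power, level with the t-test on 1–7, slightly below it on 1–10 and above it on 1–6. A log difference is also a ratio, which suits a criterion stated as a percentage. The plan names no formal normality test, so a graphical judgement could keep the t-test in place. Section II.C.1 masks the statistician to arm names.

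Much of this stands. A reader might infer that the fallback is always invalid or weaker; the figures do not support that. A reader might also expect the medians usually to tie, so that the comparison shows nothing. At the planned effect they tie in only about 6% to 10% of simulated trials, and a rank-sum test does not need them to differ. Figures built on a 5-point scale carry no weight, because that scale cannot produce the planned mean and SD.

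The defence does not supply a normality criterion or a rule for choosing between the fallbacks. Masking limits selection by favoured direction, but not selection by p-value. The log ratio compares geometric means, while the 20% was set on arithmetic means. The charitable reading of the log rule is still the one that worsens skew and costs power.

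**Conclusion.** The concern holds in a bounded form. As worded, one branch of the primary analysis cannot be executed, and the choice among the others is left until the data are seen.

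Three results need no simulation: the log of a mean is not a transformation, the criterion and selection rule are absent, and the log and median branches do not estimate the mean difference that the trial is sized on.

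The other sizes rest on assumed scales and score shapes at the planned means and SD. Logging each score costs about 1.5 points of power on 1–10 (79.9 − 78.4), 6 on 1–7 (79.7 − 73.3) and 18 on 1–6 (78.3 − 60.3). Type I error of about 6% to 7% is a worst case, reached only if the smaller p-value is always reported. That the fallback would in practice become the primary analysis depends on a formal test such as Shapiro-Wilk being used, which the plan does not say.

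A reader might go further and infer that the trial is underpowered or its sample size wrong. It is not: 56 per group reproduces and suits the t-test on raw scores. Because the rule decides the single success criterion, it should be corrected before any outcome data are examined.

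**What to change.** In V.A, delete the normality condition and the log option. State one primary analysis: the difference in mean satisfaction, immediate skin-to-skin minus control, with a two-sided 95% CI and p-value from a Welch t-test, or the equivalent linear model, on the raw scores whatever their distribution. Name the Wilcoxon rank-sum test or a proportional-odds model as a sensitivity analysis only. Apply the same rule to the pain score.

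Alongside this, state the number of points and range of both scales in II.E.1. Also say that the regression V.A triggers on observed baseline differences is supportive, so that it does not reopen the choice of primary result.

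The cost is a few sentences. No further data are needed and N stays at 112: simulated power of the t-test on discrete scores is 78.3% to 79.9%, with type I error of 4.3% to 5.3%.

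### Covariate adjustment of the primary outcome depends on an undefined judgement of baseline imbalance, so the data can decide which result is primary, and precision is lost if the covariates predict satisfaction

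*Combined protocol and SAP*

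**What the plan says.** Section V.B names the primary outcome: "Primary outcome is maternal satisfaction". Section V.A then describes its analysis in three steps.

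- Default: "Differences in satisfaction and pain scores between study groups will be assessed using t-tests if the data is normally distributed".
- If normality fails: "If not normally distributed, data will be adjusted by taking the log of the mean scores, or a non-parametric comparison of medians will be conducted".
- Adjustment: "If any clinically important differences exist between the experimental and control groups at baseline, a linear regression model will be constructed", so that group differences can be controlled.

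Section V.A also contains a general sentence on group comparisons, "Differences between study groups will be assessed using chi-square and t-tests for categorical and continuous variables, respectively". It follows the sentence on demographics but does not say which variables it covers.

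The document does not say how large a baseline difference must be to count, which variables are examined, who decides, or whether the decision comes before outcomes are seen. It does not say whether the regression replaces the t-test or stands beside it. Section II.C.1 adds one safeguard: "We do plan to blind the statistician to the treatment", by coding the arms A and B.

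**The concern.** There are two separate problems.

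First, the primary result is not fixed. Two analyses of satisfaction are possible, adjusted and unadjusted, and an undefined judgement stands between them. The normality step adds another open choice. If someone can see both results before settling on one, the nominal 5% error rate is no longer assured.

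Second, the trigger looks at the wrong thing. In a properly randomised trial, baseline differences arise by chance. Adjustment helps when the covariate predicts the outcome, whether or not it happens to be imbalanced. A rule that waits for imbalance leaves a prognostic covariate out of most trials in which it would have sharpened the estimate. The planned sample size only just reaches 80% power, so that precision is worth having.

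**Working it through.** **Inputs from Section II.C.2.** Control mean 4.0, experimental mean 4.8, SD 1.5 in both groups, alpha 0.05 (taken as two-sided), power 80%, 56 per group.

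**Assumptions, not in the documents.** One continuous baseline covariate with correlation r to satisfaction, r = 0.2 to 0.5; a trigger when the standardised mean difference (SMD) between arms exceeds 0.25.

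**1. The plan's own figure.** Difference = 4.8 − 4.0 = 0.8. Standard error = 1.5 × √(2/56) = 0.2835. Power = Φ(0.8/0.2835 − 1.96) = Φ(0.862) = 80.6%. The same formula solved for n gives 56 per arm, 112 in total, so the stated size reproduces. The t-based version gives 79.9% at 56 per arm. This calculation assumes an unadjusted comparison.

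**2. What adjustment can add.** A covariate with correlation r reduces the residual SD to 1.5 × √(1 − r²). At r = 0.4 this is 1.5 × √0.84 = 1.375, and power = Φ(0.8/(1.375 × √(2/56)) − 1.96) = Φ(1.12), about 87%. The simulated value below is slightly lower because it uses the t distribution and lets arm sizes vary.

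**3. How often the trigger fires.** P(|SMD| > 0.25) = 2 × (1 − Φ(0.25/√(2/56))) = 2 × (1 − Φ(1.323)) = 18.6%. With one covariate, about four trials in five would stay unadjusted whatever the covariate's value as a predictor.

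**4. Power of the three strategies** (simulation, n = 112, simple randomisation, difference 0.8, SD 1.5; separate runs agree to within about a point):

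| r | Unadjusted | Adjust only if SMD > 0.25 | Always adjust |
|---|---|---|---|
| 0.2 | 79% | 79% | 79-81% |
| 0.3 | 79% | 80% | 83% |
| 0.4 | 80% | 82% | 86% |
| 0.5 | 80% | 83% | 90% |

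At r = 0.4 the conditional rule recovers 82 − 80 = 2 of the 86 − 80 = 6 points available; at r = 0.5, 3 of 10.

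A wider simulation used one or four covariates and triggers of 0.2 or 0.3 SD. The shortfall of the conditional rule against always adjusting was about 2-3 points when the covariates together explained 10% of the variance, and 4-6 points at 20%.

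**5. Type I error with one covariate.**

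- Trigger applied mechanically: about 4-5%, so no inflation.
- Better of the two models, but only when imbalance is present: about 5.2-5.8%.
- Better of the two models, chosen freely: about 6-7%.

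**The case against.** The strongest reply is that nothing promised is lost. The unadjusted test still has the planned power of about 80%. The gain from always adjusting needs a prognostic covariate, which the documents do not identify, and at r = 0.2 it is about a point. A conditional rule followed mechanically is slightly conservative. The baseline comparison could be made before outcomes are analysed, and A/B coding makes deliberate steering harder. All of this stands, and it limits the size of the point. It does not answer the gap: masked labels do not fix the model, and the text supplies no rule that could be followed mechanically.

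Three stronger readings are tempting, and the documents do not support them.

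- *That simple randomisation makes imbalance likely.* Section II.C does say "Randomization will be done by simple randomization". But P(|SMD| > 0.2) for one covariate is 29.2% under simple randomisation and 29.0% with an exact 56:56 split, so blocking alone would change almost nothing. Average power over the possible splits is 80.2% against 80.6%. Stratified blocks could balance a chosen covariate, but in an unblinded single-site trial they make allocation more predictable. That is a trade-off, and this point does not require it.
- *That the switch will usually be available.* This depends on an assumed number of covariates and an assumed cut-off. For at least one of five independent covariates, the probability is 82% at 0.2 SD, 45% at 0.3 SD and 4% at 0.5 SD. The plan fixes neither number.
- *That the written rule has a 6-7% error rate, or is applied after outcomes are known.* The 6-7% needs a free choice between models regardless of balance, whereas the text allows regression only when a difference exists. On timing the text is silent.

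**Conclusion.** The point holds as a defect of pre-specification with a conditional cost in power. Section V.A leaves the choice between an adjusted and an unadjusted primary result to an undefined judgement, and bases adjustment on chance imbalance when it should rest on prognostic value.

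Under the stated assumptions, always adjusting gains over the conditional rule about 83 − 80 = 3 points of power at r = 0.3, 86 − 82 = 4 at r = 0.4 and 90 − 83 = 7 at r = 0.5, and little or nothing at r = 0.2 or below. Any excess type I error comes from discretion, not from conditional adjustment as such. With one covariate it is small if discretion is confined to imbalanced trials. With more models to choose from it grows: free choice among unadjusted, triggered and fully adjusted results, with one or four covariates, gave about 6.3-8.1%.

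The correction should be made before outcome data are examined. It does not call the sample size or the randomisation method into question.

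**What to change.** Replace the conditional sentence in Section V.A with wording such as:

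> The primary analysis of satisfaction is a linear model on arm plus two or three named covariates known before birth from the chart and chosen in advance as likely to predict satisfaction (for example previous cesarean and maternal age), fitted regardless of observed balance. The unadjusted comparison, with any log-transformed or non-parametric version, is a sensitivity analysis.

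The second sentence is needed because the normality step would otherwise still offer competing primary analyses. The two covariates are illustrations: the documents do not identify them as prognostic, and the investigators should choose the list and record it before outcomes are seen.

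The cost is a short change of text and one degree of freedom per covariate. Covariates available from the chart add no burden for participants, and the total of 112 does not change. If the chosen covariates turn out not to predict satisfaction, the loss is only those few degrees of freedom.
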